8 STUDY TREATMENTS

Dupilumab (Dupixent ®)

8.1 Supply of Study Drug at the Site

Regeneron and Sanofi-Genzyme will ship the study drug to the investigational sites. The

study drug is supplied in cartons containing either two 300 mg/2 mL solution pre-filled syringes with needle shield or 2 pre-filled syringes. Each kit of study drug will be labeled with the required FDA warning statement, the protocol number, and directions for use and storage.

8.2 Storage

Dupilumab must be refrigerated at 36°F to 46°F (2°C to 8°C) in the original carton to protect from light. The medication will be kept in a temperature-monitored refrigerator at the study site. If necessary, pre-filled syringes may be kept at room temperature up to 77°F (25°C) for a maximum of 14 days. The product will be kept in the original carton until the time of use.

8.3 Dosage/Dosage Regimen

Dupilumab will be administered at an initial dose of 600 mg subcutaneously followed by 300mg subcutaneously through the study, which is the FDA-approved and recommended dose for dupilumab. There is no weight-based dosing. The dosing schedule will be as follows: dupilumab 600mg subcutaneously once at week 0, followed by dupilumab 300 mg subcutaneously every other week until week 50.

8.4 Administration Instructions

All doses of study treatment will be administered at the study site after the study assessments for the visit have been completed at visits occurring between week 0 and 4, as well as weeks 8, 12, 16, 24, 36, and 44. After week 4 subjects will administer the medication independently every other week (weeks 6, 10, 14, 18, 20 22, 26, 28, 30, 32, 34, 38, 40, 42, 46, 48, and 50) only after they have shown the competency to self-administer the treatment outside of the study site. The medication will be administered via subcutaneous injection into the thigh or abdomen, except for the 2 inches (5 cm) around the navel. The upper arm can also be used if a caregiver administers the injection. There will be no medication given after week 50.

The subject should be instructed to contact the investigator if he/she is unable for any reason to attend a study visit as scheduled. All dates and times of injections done to the subject during the study must be recorded on the Dosage Administration Record CRF. The investigator will promote compliance by instructing the subject to attend the study visits as scheduled and by stating that compliance is necessary for the subject's safety and the validity of the study.

8.5 Study Drug Accountability

The qualified site personnel will maintain an accurate record of the shipment and dispensing of study treatment in a treatment accountability log. All study treatment kits assigned to the subject during the study will be recorded.

8.6 Measures of Treatment Compliance

Subjects will be given scheduled doses of dupilumab at each visit from visit 1 (week 0)

until visit 9 (week 44). After week 4, subjects will be given a dosing diary to record their scheduled injections administered at home every other week.

9 STUDY PROCEDURES AND GUIDELINES

A Schedule of Events representing the required testing procedures to be performed for the duration of the study is diagrammed in Appendix 1.

Prior to conducting any study-related activities, written informed consent and the Health Insurance Portability and Accountability Act (HIPAA) authorization must be signed and dated by the subject.

All clinical assessments will take place at the study site: [name]

All blood draws will take place at the UCSF Lab at Mount Zion: [name]

All patch testing will take place at UCSF Department of Dermatology, [name].

9.1 Clinical Assessments

For subjects with a diagnosis of atopic dermatitis:

9.1.1 Medical History

Relevant medical history, including history of current disease, and information regarding underlying diseases will be recorded at Screening.

1.1.2 Concomitant Medications

All concomitant medication and concurrent therapies will be documented at Screening, at every site visit, and at early termination when applicable. Dose, route, unit frequency of administration, and indication for administration and dates of medication will be captured.

9.1.3 Demographics

Demographic information (date of birth/age, gender, ethnicity, age of onset, vital signs, body mass index, body surface area, EASI, IGA, pruritus numerical rating, laboratory values (CBC with differential, BUN, Cr, AST/ALT/Alk Phos), baseline medications)) will be recorded at Screening.

9.1.4 Physical Examination

A complete physical examination will be performed by either the investigator or a sub-investigator who is a physician at screening and weeks 0, 12, 24, and 52. New abnormal physical exam findings must be documented and will be followed by a physician or other qualified staff at the next scheduled visit.

9.1.5 Vital Signs

Body temperature, blood pressure, pulse and respirations will be performed after resting for 5 minutes at all site visits.

9.1.6 Adverse Events

Information regarding occurrence of adverse events will be captured throughout the study. Duration (start and stop dates and times), severity/grade, outcome, treatment and relation to study drug will be recorded on the case report form (CRF).

9.1.7 EASI and IGA

Eczema Area and Severity Index (EASI) and Investigator Global Assessment (IGA) will be completed at screening and weeks 0, 2, 4, 8, 12, 16, 24, 36, 44, and 52.

9.1.8 Pruritus Numerical Rating

Pruritus numerical rating will be completed at weeks 0, 2, 4, 8, 12, 16, 24, 36, 44, and 52.

9.1.9 Photography

Photographs (full front and back) will be taken at weeks 0, 2, 4, 12, and 52.

9.2 Clinical Laboratory Measurements

9.2.1 Hematology

Blood will be obtained and sent to the clinical hematology lab for a complete blood count (hemoglobin, hematocrit, red blood cell count, white blood cell count, white blood cell differential, and platelet count) determinations for assessment of systemic evidence for infection and/or inflammation at Screening.

9.2.2 Blood Chemistry Profile

Blood will be obtained and sent to the clinical chemistry lab for determination of electrolyte levels, serum BUN, creatinine, AST, ALT, and alkaline phosphatase at screening.

9.2.3 Pregnancy Test

A urine pregnancy test will be obtained at the study site for female subjects of childbearing age at screening and weeks 0, 4, 8, 12, 16, 24, 36, 44, and 52.

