2.2 Risk / Benefit Assessment

Details of the risk and benefits of dupilumab are outlined in the Prescribing Information. The most common adverse effects (incidence $\geq 1\%$) of dupilumab include injection site reactions, conjunctivitis, blepharitis, oral herpes, keratitis, eye pruritus, other herpes simplex infection, and dry eye. Other adverse effects include hypersensitivity reactions, including generalized urticarial and serum sickness or serum sickness-like reactions.

The risk to subjects in this trial will be minimized by compliance with the inclusion/exclusion criteria, proper study design, and close clinical monitoring.

In regards to skin biopsy procedures, as in any surgical procedure, there are certain inherent risks including bleeding, post-operative pain, infection, reactions to sutures, anesthetics or topical antibiotics, and scarring. All reasonable efforts will be made to minimize the possibility of these potential complications.

In regard to patch testing, in rare cases there may be blistering reactions, in highly allergic patients. It is possible in these instances for scarring to occur at the site of the offending allergen. Sometimes, particularly in patients with photodamaged skin temporary bruising can occur with removal of the tape from the patches. Patch testing, in rare circumstances, can lead to excited skin syndrome (typically in patients who have significant active dermatitis at the time of testing). To mitigate this, patients deemed to have no clear areas for testing due to significant active dermatitis will not be patch tested. Patients who are pregnant will also be excluded, as patch testing has not been studied in this population. We believe there is only minimal risk to those participating in any and all parts of this study. We also believe that the minimal risk is reasonable for the benefits gained by a better understanding of how dupilumab affects contact allergy. Additionally, patients will receive patch testing and allergen avoidance which is of immense benefit to improving their skin disease and quality of life going forward.

The benefit to subjects is that they will be receiving an approved therapy for moderate-to-severe atopic dermatitis. Although it cannot be guaranteed, dupilumab has shown to be safe and effective in moderate-to-severe atopic dermatitis. An additional benefit to patients is that they are contributing to society by helping the enhancement of science.

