9.2.6 Pre-treatment and post-treatment dupilumab testing

Pre-dupilumab patch testing:

Each of the 15 patients will be patch tested to a core series of allergens (see below). The allergens will be applied to the back of the patient using Finn Chambers (SmartPractice, Phoenix, AZ) on Scanpor tape (Norgesplaster Alpharma AS, Vennesla, Norway). More Scanpor tape will be applied over the patches to secure them to the back. 48 hours later the patient will return for patch removal and photography. Readings will be graded as follows: ? (weak/doubtful), + (mild), ++ (strong), or +++ (very strong) on the basis of degrees of induration, papules, vesicles, and/or spreading beyond the disc space. A final determination of “allergic/positive” or “not allergic” will be determined on the basis of the pattern (crescendo/decrescendo), patch test appearance, and known characteristics of that allergen. For example, a weak/doubtful (macular erythema) reaction to a formaldehyde-releasing agent could be determined to be an allergic/positive reaction in the setting of multiple or stronger reactions to related formaldehyde-releasing allergens. The clinical relevance of the positive patch test reaction will be determined using the patient’s history and clinical skin examination. Current relevance is defined as definite (a use test with the suspected item containing the putative allergen was positive, or a patch test to the object or product was positive), probable (the allergen can be verified as present in known skin contactants, and the clinical presentation was consistent), or possible (the patient is exposed to circumstances in which skin contact with materials known to contain the allergen was likely to occur). Past relevance will also be indicated. At the final visit the patient will be counseled regarding allergen avoidance.

Post-dupilumab patch testing:

After 6 months of dupilumab therapy the patient will undergo a second round of patch testing, to the same core series of allergens and using the same procedures described above. If new allergens are identified, additional avoidance counseling will occur.

Timing and logistics:

Each patch test will require 2 three-part patient visits. Application of allergens will take approximately 20 minutes. Removal and photography (48 hours later) approximately 10 minutes. Final reading (120 hours after placement) and allergen avoidance counseling will occur at the final visit (approximately 30 minutes).

ACD Core 80 Series

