10.1 Visit 0 (Screening)

1. Review inclusion/exclusion criteria.
2. Review the study with the subject and obtain written informed consent and HIPAA authorization and assent, if appropriate.
3. Assign the subject a unique screening number.
4. Record demographics data.
5. Record medical history, including a history of atopic dermatitis, diagnosis date, and prior treatments for atopic dermatitis.
6. Record concomitant medications.
7. Perform and record vital signs.
8. Perform a complete physical examination.
9. Perform EASI and IGA.

10. Perform pruritus numerical rating.
11. Collect blood for clinical laboratory tests (CBC, serum electrolytes, BUN, Creatinine, AST, ALT, alkaline phosphatase).
12. Perform urine pregnancy test (if applicable).

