10.2 Visit 1: PRE-TREATMENT PATCH TESTING

1. Application of contact allergens (20 minutes).
2. 48 hours later: removal of allergens and photography (30 minutes).
3. 120 hours later: final reading of allergens (10 minutes) and allergen avoidance counseling (approximately 30 minutes).

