10.10 Visit 9 POST-TREATMENT PATCH TESTING (between weeks 24 and 36)

1. Application of contact allergens (20 minutes).
2. 48 hours later: removal of allergens and photography (30 minutes).
3. 120 hours later: final reading of allergens (10 minutes) and allergen avoidance counseling (approximately 30 minutes).

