APPENDIX 1. EVALUATION SCHEDULE

Visit number	0	1	2	3	4	5	6	7	8	9	10	11	12	
Time of Visit	Screening	Patch testing	wk	Patch testing	wk	wk	wk	Early termination						
			0	2	4	8	12	16	24		36	44	52	
Inclusion/Exclusion criteria	X													
Informed consent	X													
Review medical history	X													
Physical examination	X		X			X		X				X		X
Vital Signs	X		X	X	X	X	X	X	X		X	X	X	X
EASI and IGA	X		X	X	X	X	X	X	X		X	X	X	X
Pruritus Numerical Rating			X	X	X	X	X	X	X		X	X	X	X
Laboratory assessments*	X													
Urine Pregnancy	X		X		X	X	X	X	X		X	X	X	X
Adverse events			X	X	X	X	X	X	X		X	X	X	X
Review con meds	X		X	X	X	X	X	X	X		X	X	X	X
Biopsy Procedures			X	X	X		X							
Skin swabs and stool sample			X	X	X		X					X		
Photography			X	X	X		X					X		X
Dispense study medication			X	X	X	X	X	X	X		X	X		
Patch testing		X								X				

*CBCPD, BMP, BUN, Cr, AST/ALT/Alk Phos

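### Section 2.2 excludes pregnant patients on patch-testing grounds, but no pregnancy test is scheduled at either patch-test visit; at Visit 9 the latest result is nominally about 2 weeks old and at most about 11 to 12

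*Combined protocol and SAP*

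**What the plan says.** **The exclusion.** Section 2.2, in the paragraph on patch-testing risks, says: "Patients who are pregnant will also be excluded, as patch testing has not been studied in this population". The sentence just before it withholds patch testing from patients without clear skin.

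**The two rounds.** Section 10.2 is headed "PRE-TREATMENT PATCH TESTING" and comes before week 0. For the second round, section 9.2.6 says: "After 6 months of dupilumab therapy the patient will undergo a second round of patch testing". Section 10.10 gives its window in the heading: "POST-TREATMENT PATCH TESTING (between weeks 24 and 36". Each round runs five days, ending with the step described as "Final reading (120 hours after placement" in 9.2.6.

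**The pregnancy tests.** Section 9.2.3 schedules a urine test at the study site for women of childbearing age "at screening and weeks 0, 4, 8, 12, 16, 24, 36, 44, and 52". The visit lists carry it as "Perform urine pregnancy test (if applicable" at screening (10.1, item 12) and again at week 24 (10.9, item 7). Sections 10.2 and 10.10 list only application, removal with photography, and reading with counselling. In Appendix 1 the row "Urine Pregnancy" is blank under Visits 1 and 9.

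**Stopping for pregnancy.** Section 12.1 names a positive pregnancy test as a possible reason to stop study drug. It then asks that everyone who stops attend an early discontinuation visit and be urged to finish the rest of the schedule. Section 12.2 gives subjects who withdraw a final visit with the procedures of their next scheduled visit. Neither section mentions patch testing.

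**The concern.** The reason in 2.2 concerns the procedure, and the procedure is done twice, the second time about six months into treatment. A check at entry cannot apply that reason to the second round. Staff at Visits 1 and 9 have no scheduled test on the day and must rely on the previous visit's result or on what the subject tells them. If a woman conceives after that test and does not know it, the plan followed to the letter would patch test her against its own exclusion.

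The stake is participant safety. Section 2.2 gives lack of study as its reason and states no fetal harm. A smaller matter is that someone reading 12.1 or 12.2 alone would not see that a subject who stopped for pregnancy must skip the second round.

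**Working it through.** The plan states no figure for the age of the pregnancy result at patch testing, so there is none to reproduce. The check is a comparison of schedules plus subtraction.

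**Inputs**
- Test weeks from baseline on: 0, 4, 8, 12, 16, 24, 36, 44, 52 (9.2.3), preceded by one test at screening.
- Visit 9 window: weeks 24 to 36 (10.10).
- Nominal timing of the second round: after six months (9.2.6). Taking this as week 26 (52 / 2) is an assumption.
- Length of a round: 120 hours = 5 days = 5/7 = 0.71 weeks (9.2.6).

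**Step 1: do the sources agree?** Section 9.2.3, the lists in 10.2 and 10.10, and the Appendix 1 row all place no pregnancy test at Visits 1 and 9. Three concordant places make a table-reading error unlikely.

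**Step 2: gaps between successive tests from week 0.** 4, 4, 4, 4, 8, 12, 8, 8 weeks. The longest is 36 - 24 = 12 weeks, and Visit 9 falls inside it.

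**Step 3: age of the week 24 result when allergens are applied at Visit 9.** Age = week of application - 24.

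| Timing of application | Age of result |
|---|---|
| Start of window, week 24 | 24 - 24 = 0 weeks |
| Six months, taken as week 26 | 26 - 24 = 2 weeks |
| Latest, if the 120-hour reading must fall by week 36 | 12 - 0.71 = 11.3 weeks |
| Latest, if only application must fall by week 36 | 36 - 24 = 12 weeks |

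**Step 4: age of the screening result at Visit 1.** The last test is at screening and the next is at week 0, after the round. No interval from screening to Visit 1 is stated, so the age cannot be computed.

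**Step 5: how the stopping rules meet 2.2.** The termination visit (10.14) includes a urine test and no patch testing, so it raises no conflict. The overlap lies in what follows. A subject who stops drug before Visit 9 still has that visit ahead of her under 12.1. If she withdraws between the week 24 visit and Visit 9, her next scheduled visit under 12.2 is the patch-test visit. Section 2.2 would bar her, but neither section points to it.

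**Step 6: with a test at application.** The result would be 0 days old in both rounds. A test at week w would also split the 12-week gap into w - 24 and 36 - w weeks.

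**The case against.** **The sentence in 2.2 may only restate the entry exclusion.** Section 6.3 excludes pregnant women (no. 17) and women unwilling to use effective contraception (no. 18), inclusion criterion 8 in 6.2 covers the same ground, and screening includes a test. This reading is possible. It fits less well, because the sentence sits among patch-test risks and gives a patch-test reason.

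**A scheduled test already precedes each round.** This is true, and nothing in the documents demands a same-day test. A reader might infer that the schedule breaks a stated requirement for one. It does not: the exclusion is stated without a means of checking it when it applies.

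**Twelve weeks is the extreme.** This stands. A reader might take 12 weeks as the usual age of the result. Section 9.2.6 points to about six months, so about 2 weeks is the nominal figure.

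**The plan accepts the same interval for the drug.** Self-injections at weeks 26, 28, 30, 32 and 34 (8.4) also go without a scheduled pregnancy test, with contraception as the safeguard. That is a fair point on proportion. But section 2.2 makes its own commitment about patch testing, and a test at Visit 9 would shorten the untested interval for the drug as well.

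**Section 12.1 does not send pregnant women to patch testing.** A reader might infer that it does, since it makes no exception. The documents do not support this. A woman who stopped for a positive test is known to be pregnant, and 2.2, read as a patch-testing exclusion, already bars her. A specific exclusion would ordinarily govern a general encouragement. What remains is a missing cross-reference.

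**Conclusion.** The point holds as a minor safety refinement. No pregnancy test is scheduled at Visit 1 or Visit 9, although 2.2 excludes pregnant patients for a patch-testing reason. At Visit 9 the latest scheduled result is about 2 weeks old on the nominal timing and at most about 11 to 12 weeks old. At Visit 1 its age is unspecified. The stopping-rule point is secondary and a matter of clarity.

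This rests on reading 2.2 as applying to each round, and the nominal figure rests on taking six months as week 26. The number of women of childbearing potential among the 15 subjects is not given. With contraception required, few would be expected to be affected, but no count can be calculated. A reader might also infer a known hazard to the fetus, which the documents do not state. The primary endpoint, its analysis and the sample size are unaffected.

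**What to change.** Add a urine pregnancy test before allergens are applied at Visit 9, and likewise at Visit 1. Enter it in 9.2.3, as the first item in 10.2 and 10.10, and in the urine row of Appendix 1. As a clarification, add one line to 12.1 and 12.2: a subject with a positive pregnancy test is followed up but is not patch tested.

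The cost is one urine dipstick at each of two existing visits per woman of childbearing potential, plus a few lines of text. Section 9.2.3 places urine tests at the study site, and section 9 lists the patch-testing location separately. The documents do not show whether these are the same place, so kits may need to be stocked at the patch-testing location.

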9.2.4 Microbiome Sampling

Sterile-technique skin swabbing and collection of stool samples will be performed at weeks 0, 2, 4, 12, and 52. Specimens will be stored at -80 C for future analysis.

9.2.5 Skin biopsy procedure

At weeks 0, 2, 4, and 12, four standard 5mm punch biopsies (the approximate size of a pencil-end eraser) will be performed. Of the biopsies performed at each visit, 3 will be from atopic dermatitis lesional skin and 1 will be from non-lesional (clear) skin. After selecting biopsy sites on trunk or extremities (subject preference), the area will be

cleansed with an antiseptic solution and a numbing medication (lidocaine or lidocaine with epinephrine) will be injected to the biopsy area. Each 5mm piece of skin will be removed via punch biopsy and a sterile gauze pad will be placed over the site to control bleeding. The biopsy site may be closed with a stitch. The parents will be provided with post-biopsy care instructions. All standard of care guidelines and sterile technique will be used. These specimens will be analyzed by CyTOF and RNAseq.

9.2.6 Pre-treatment and post-treatment dupilumab testing

Pre-dupilumab patch testing:

Each of the 15 patients will be patch tested to a core series of allergens (see below). The allergens will be applied to the back of the patient using Finn Chambers (SmartPractice, Phoenix, AZ) on Scanpor tape (Norgesplaster Alpharma AS, Vennesla, Norway). More Scanpor tape will be applied over the patches to secure them to the back. 48 hours later the patient will return for patch removal and photography. Readings will be graded as follows: ? (weak/doubtful), + (mild), ++ (strong), or +++ (very strong) on the basis of degrees of induration, papules, vesicles, and/or spreading beyond the disc space. A final determination of “allergic/positive” or “not allergic” will be determined on the basis of the pattern (crescendo/decrescendo), patch test appearance, and known characteristics of that allergen. For example, a weak/doubtful (macular erythema) reaction to a formaldehyde-releasing agent could be determined to be an allergic/positive reaction in the setting of multiple or stronger reactions to related formaldehyde-releasing allergens. The clinical relevance of the positive patch test reaction will be determined using the patient’s history and clinical skin examination. Current relevance is defined as definite (a use test with the suspected item containing the putative allergen was positive, or a patch test to the object or product was positive), probable (the allergen can be verified as present in known skin contactants, and the clinical presentation was consistent), or possible (the patient is exposed to circumstances in which skin contact with materials known to contain the allergen was likely to occur). Past relevance will also be indicated. At the final visit the patient will be counseled regarding allergen avoidance.

Post-dupilumab patch testing:

After 6 months of dupilumab therapy the patient will undergo a second round of patch testing, to the same core series of allergens and using the same procedures described above. If new allergens are identified, additional avoidance counseling will occur.

Timing and logistics:

Each patch test will require 2 three-part patient visits. Application of allergens will take approximately 20 minutes. Removal and photography (48 hours later) approximately 10 minutes. Final reading (120 hours after placement) and allergen avoidance counseling will occur at the final visit (approximately 30 minutes).

ACD Core 80 Series

1. Benzocaine, 5.0% pet.
2. 2-Mercaptobenzothiazole, 1.0% pet.
3. Colophonium (rosin), 20.0% pet.
4. 4-phenylenediamine base, 1.0% pet.
5. Benzyl Alcohol 10.0%
6. Fragrance mix II, 14.0% pet.
7. Lanolin alcohol (Amerchol L101), 50% pet.
8. Carba mix, 3.0% pet.
9. Neomycin sulfate, 20.0% pet.
10. Thiuram mix, 1.0% pet.
11. Oleamidopropyl Dimethylamine 0.1% aq.
12. Ethylenediamine dihydrochloride, 1.0% pet.
13. Bisphenol A epoxy resin, 1.0% pet.
14. Quaternium-15, 2.0% pet.
15. 4-tert-butylphenol formaldehyde resin, 1.0%
16. Ethylhexyl Salicylate, 5.0% pet.
17. Fusidic acid sodium salt, 2% pet.
18. Potassium dichromate, 0.25% pet.
19. Myroxylon Pereirae resin (Balsam of Peru)
20. Nickel sulfate hexahydrate, 2.5% pet.
21. Diazolidinyl urea (Germall II), 1.0% pet.
22. DMDM hydantoin (Germall 115), 1.0% pet.
23. Imidazolidinyl urea, 2.0% pet.
24. Bacitracin, 20.0% pet.
25. Mixed dialkyl thioureas, 1.0% pet.
26. Methylchloroisothiazolinone/methylisothiazolinone,
27. Paraben mix, 12.0% pet.
28. Cinnamal (Cinnamic aldehyde), 1.0% pet.
29. Fragrance mix I, 8.0% pet.
30. Amidoamine(stearamidopropyl dimethylamine)
31. 2-Bromo-2-nitropropane -1,3-diol (Bronopol)
32. Sesquiterpenelactone mix, 0.1% pet.
33. 2-Hydroxyethyl methacrylate, 2.0% pet.
34. Propylene glycol, 30.0% aq.
35. Benzophenone-3 (Oxybenzone)
36. Chloroxylenol (4-Chloro-3,5-xylenol), 1.0% pet.
37. Isopropyl myristate, 20.0% pet.
38. Methylisothiazolinone, 0.2% aq. (2000 ppm)
39. Desoximetasone, 1.0% pet.
40. Methylbromoglutaronitrile/Phenoxyethanol, (MDBGN/PE) (Euxyl K 400), 2.0% pet
41. Triethanolamine, 2% pet.
42. Tocopherol (DL-a-Tocopherol),, 100.0%
43. Iodopropynyl butylcarbamate, 0.5% pet.
44. Ethyl acrylate, 0.1% pet.
45. Polysorbate 40, 5% pet.
46. Tosylamide /formaldehyde resin, 10.0% pet.
47. Methyl methacrylate, 2.0% pet.
48. Cobalt (ii) chloride hexahydrate, 1.0% pet.
49. Tixocortol-21-pivalate, 1.0% pet.

50. Budesonide, 0.1% pet.
51. Hydroperoxide of linalool, 1% pet.
52. Disperse blue mix 124/106, 1.0% pet.
53. Propolis, 10.0% pet.
54. Lidocaine-HCl, 15.0% pet.
55. Hydroperoxied of limonene, 0.3 pet.
56. Clobetasol-17-propionate, 1.0% pet.
57. Cocamidopropyl betaine, 1.0% aq.
58. Formaldehyde, 2% aq.
59. Disperse orange 3, 1% pet.
61. Cocamide DEA
62. Compositae mix, 6.0% pet.
63. 2-n-octyl-4-isothiazolin-3-one, 0.1% pet.
64. Melaleuca Alternifolia (tea tree leaf oil)
65. Cananga Odorata Flower oil (ylang –ylang oil)
66. Benzyl salicylate, 10% pet.
67. Disperse yellow 3, 1% pet.
68. Decyl glucoside, 5.0% pet.
69. Mercapto mix, 1.0% pet.
70. Glyceryl thioglycolate, 1% pet.
71. Benzoyl peroxide, 1% pet.
72. Dibucaine hydrochloride, 2.5% pet.
73. 2-tert-buyl-4-methoxylphenol, 2% pet.
74. Isoamyl-p-methoxycinnamate, 10% pet.
75. Ethyleneurea, melamine formaldehyde mix, 5%
76. Gold sodium thiosulfate, 0.5% pet.
77. Hydroxyisohexyl 3-cyclohexene carboxaldehyde, 5% pet.
78. Texile mix, 6.6% pet.
79. Glutural, 0.5% pet.
80. Diphenylguanidine, 1.0% pet.

